Investigating the Efficacy of a Fractionated 1927nm Laser for Diffuse Pigmentation and Actinic Changes

NCT05226104

30 September 2022

SPONSOR	UT Southwestern Department of Plastic Surgery
TESTING & ADMINISTRATIVE FACILITY	UT Southwestern Medical Center [name]
PRINCIPLE INVESTIGATORS	[name], MD
SUB-INVESTIGATORS	[name], MD [name], BS

1. Background

Melasma is an acquired skin condition defined by symmetric hyperpigmentation, typically occurring on the face. It arises from hyperfunctional melanocytes that deposit excess melanin into the epidermis and dermis, resulting in irregular light to greyish brown macules on the skin.¹⁻³ Studies have shown that the estimated prevalence in the general population exists at about 1% while higher-risk populations can reach a prevalence of up to 50%.^{4,5} The condition is also noted to have female predominance, particularly during reproductive years.^{1,6,7} Pathogenesis is multifactorial and not yet fully understood; however common etiologic factors that play a role include sun exposure, genetic influences and female sex hormones. Hormonal influences play a significant role, most notably seen by the increased prevalence of melasma amongst pregnant women or those who use hormonal therapies such as hormonal contraceptives.⁸⁻¹² Melasma can occur in all skin types, however, more commonly affects darker skin types.¹³

MOXI is a fractionated 1927 wavelength thulium non-ablative laser (f1927) developed to reduce unwanted pigment, improve skin texture and tone and promote new cell growth. The fractionated 1927 nm thulium non-ablative laser is suitable for targeting epidermal lesions and has been shown to be effective in resurfacing photoaged skin as well as addressing pigmented lesions without exacerbation.¹⁸⁻²⁵ Thus it is a very effective option for addressing pigment concerns and the treatment itself requires less downtime than more aggressive laser procedures.

This study intends to evaluate the clinical performance of f1927 for the treatment of diffuse pigmentation including melasma. We hypothesize that the treatment will produce a statistically significant improvement in the appearance of hyperpigmentation over the course of 30 days, followed by 1-month and 3-month post-treatment visits when compared to baseline.

2. Purpose

This single-center clinical trial is being conducted over the course of 30 days followed by 1-month and 3-month follow-up visits. The primary objective of this study is to assess the efficacy of f1927 when used by men and women with diffuse hyperpigmentation and/or melasma.

3. Concise Summary of Project

3.1. Clinical Study

This is a single-site, non-randomized, non-controlled study at UT Southwestern Medical Center at Dallas in the Department of Plastic Surgery designed to follow up to 30 qualified and consenting subjects receiving

f1927 treatments under an IRB approved protocol

[REDACTED]

[REDACTED]

[REDACTED]

[REDACTED]

These patients will receive treatment using a f1927 device and will be treated twice over the affected areas, once each month for a total of two months, followed by two follow-up visits at 1-month and 3-months post-treatment.

[REDACTED]

[REDACTED]

[REDACTED]

[REDACTED] A quantitative assessment of the effects of treatment will be performed using VISIA and Vectra H2 3D facial skin analysis at 1-month and 3-months post-treatment.

[REDACTED]

[REDACTED]

3.2. Primary Endpoints

- Assessment of improvement in overall facial hyperpigmentation using quantitative measurements provided by VISIA and Vectra H2 3D analysis of photos obtained at Baseline, 1-Month and 3-Months post-treatment to evaluate the efficacy of f1927 treatments
 - Calculate percent change from baseline in visualization and numeric analysis of brown and red areas utilizing the Facial Skin Analysis on Canfield's Imaging Systems
- Clinician assessment of pigmentation improvement using the Physician's Global Assessment Scale

3.3. Secondary Endpoints

- Monitoring incidence, severity, and relatedness of adverse events throughout the study.

4. Test Material Information

4.1. Study Device Description

The following devices will be evaluated during the study:

Proprietary Name	Device Description	Regulatory Information
Sciton MOXI	Aesthetic device that utilizes a fractionated laser to treat uneven pigmentation and heal photodamaged skin	Class II 510(K) Number: N/A Regulation Number:878.4810

5. Study Population and Enrollment

5.1. Subject Enrollment

Healthy subjects who are interested in treatment for diffuse pigmentary changes will be recruited for the study through recruitment flyers and social media posts. [REDACTED]

[REDACTED]

[REDACTED]

[REDACTED]

[REDACTED]

[REDACTED] Potential subjects will have the study explained to them, will be asked about their willingness to be involved in the study, and their willingness to sign an informed consent form.

5.2. Informed Consent Form

An IRB-approved informed consent form (ICF), explaining the purpose, design, risks and duration of the study, will be given to each candidate subject before participation in any study procedures. The candidate subject will be given as much time as needed to read the ICF and will have the opportunity to have any study-related questions answered to their satisfaction prior to signing the ICF [REDACTED]

[REDACTED]

[REDACTED]

[REDACTED]

[REDACTED]

[REDACTED]

5.3. Subject Identification

[REDACTED]

[REDACTED]

[REDACTED]

[REDACTED]

5.4. Eligibility Criteria

Inclusion Criteria

1. Healthy male and female adults between 20-75 years of age.
2. Fitzpatrick skin type I-IV.
3. Individuals deemed by the Investigator to have a significant amount of pigmentation/melasma and that desire correction of this condition.
4. Individuals willing to withhold aesthetic therapies, or other therapies judged to potentially impact results to the treatment areas for the duration of the study.
5. Women of childbearing potential who agree to take a urine pregnancy test at the Screening visit or when deemed by Investigator. Women of childbearing potential must have a negative urine pregnancy test and must not be lactating at Screening. Women must be willing and able to use an acceptable method of birth control (see below) during the study. Women will not be considered of childbearing potential if one of the following is documented – postmenopausal for at least 12 months prior to study, without a uterus and/or both ovaries, bilateral tubal ligation at least 6 months prior to study enrollment.

7. Individuals who can read, speak, write and understand English and who are willing to provide written informed consent.
 8. Individuals willing to sign a photography release.
 9. Individuals willing and able to cooperate with all study requirements for the duration of the study.

Exclusion Criteria

1. Fitzpatrick skin type V-VI.
 2. Known allergies to general skin care products.

18. Individuals undergoing concurrent therapy that, in the Investigator's opinion, would interfere with the evaluation of the safety or efficacy of the study devices.

25. Individuals who are unable to understand instructions or give informed consent
26. Individuals who have physical or psychological conditions which, in the opinion of the Investigator, makes them unable to complete the study per protocol (e.g., not likely to avoid other cosmetic treatments to area; not likely to stay in study for entire duration due to other commitments; or those with concomitant conditions that may develop symptoms that might confuse or confound study treatments or assessments).

6. Subject Instructions

Subjects will be asked to wash off all skincare products at least 30 minutes prior to each scheduled clinic visit using a cleanser of your choice.

Subjects will be asked to avoid extended periods of sun exposure and all use of tanning beds for the duration of the study. Extra care should be taken to wear protective clothing and avoid sun exposure from 10 AM to 4 PM.

Subjects will be encouraged to consistently use face wash, moisturizer, and sunscreen of their choosing. Subjects will be asked to refrain from using any new anti-aging, acne, and acne scar products or devices and beginning the use of any new skincare products or devices other than the assigned test material for the duration of the study.

7. Study Design

7.1. Outline of Procedures

Procedures/ Time Points:	Visit 1	Visit 2	Visit 3	Visit 4	Visit 5
	Screening (-30 to 0 days)	Baseline/ Treatment #1* (Day 0 ; \pm 3 days)	Treatment #2 (Day 30; \pm 3 days)	1-month post-treatment (\pm 3 days)	3-months post-treatment (\pm 3 days)
Informed Consent	X				
Enrollment Paperwork	X				
Medical History/ Concomitant Medications	X	X	X	X	X
Pregnancy Test	X				
MOXI Treatment		X	X		
Standard Photography	X			X	X
H2 3D and VISIA Photography	X			X	X
Physician's Global Assessment Scale				X	X
Safety Assessment		X	X	X	X

* Treatment #1 (Visit 2) activities may be conducted at the Screening visit (Visit 1)

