7.3. Screening: Visit 1 (Day 0; -14 to 0 days)

The purpose of the study, eligibility criteria and potential risks will be discussed with the potential subject.

This visit will take 30-45 minutes. Screening (Visit 1) may be combined with Visit 2.

7.4. Treatment Visits: Visit 2 (Day 0; +/-3 days) and Visit 3 (Day 30; +/-3 days)

A member of the study team will record concomitant medications and will ask subjects if they have experienced any changes in their health since the previous visit. If an adverse event (AE) is reported than the Investigator will be informed, and an AE log will be completed/updated for PI review.

The procedure will then be performed in our Plastic Surgery clinic following standard of care procedures. A trained staff member will apply a topical triple anesthetic (benzocaine, lidocaine, tetracaine) to anesthetize the areas being treated. [REDACTED]

Appropriate post-treatment care instructions will be provided as deemed appropriate by the Investigator or study staff. [REDACTED]

These visits will take approximately 1 hour.

7.5. Follow-Up Visits: Visit 4 (1-Month Post Treatment) and Visit 5 (3-Months Post Treatment)

At a minimum, all subjects will return for follow-up visits at 1 month (+/- 3 days) and 3 months (+/-3 days) after treatment.

The following activities will be performed on all study subjects during the follow-up visits:

1. The physician or study staff will ask subjects if they have experienced any changes in their health since the previous visit. Changes will be recorded accordingly. If an adverse event (AE) is reported than the Investigator will be informed, and an AE form will be completed.
 2. Subjects will acclimate to ambient temperature and humidity conditions for 15 minutes prior to any procedures being done.
 3. The physician or study staff will perform an examination of the skin in the treatment area
 4. Obtain post-treatment close up and standard photography as described in section 8.1.
 5. Obtain post-treatment photographs and measurements using the Vectra H2 3D Imaging System and VISIA Imaging System as described in section 8.1.

These visits will take about 30 minutes.

8. Assessments

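### The only scheduled pre-treatment images are taken at Screening, not at Visit 2 (Baseline/Treatment #1), and the two screening windows (30 and 14 days) contradict each other

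*Combined protocol and SAP*

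**What the plan says.** - **Imaging.** The Section 7.1 table marks Standard Photography and H2 3D and VISIA Photography at Visits 1, 4 and 5. Visit 2, headed Baseline/Treatment #1, has no imaging mark. Laser treatment is marked at Visits 2 and 3.
- **Screening window.** The Section 7.1 column heading gives "Screening (-30 to 0 days". The Section 7.3 heading gives "Screening: Visit 1 (Day 0; -14 to 0 days".
- **Combining visits.** Section 7.3 says "Screening (Visit 1) may be combined with Visit 2", and the Section 7.1 footnote says "Treatment #1 (Visit 2) activities may be conducted at the Screening visit (Visit 1". Both permit it; neither requires it.
- **Later windows.** Section 7.4 is headed "Treatment Visits: Visit 2 (Day 0; +/-3 days) and Visit 3 (Day 30; +/-3 days". Section 7.5 says that "all subjects will return for follow-up visits at 1 month (+/- 3 days) and 3 months (+/-3 days) after treatment".
- **Use of the baseline image.** Section 3.2 bases the imaging endpoint on Baseline, 1-month and 3-month photographs. Section 9 makes a paired comparison with baseline, on Vectra H2 3D data, the primary outcome. Score 6 of the Physician's Global Assessment (PGA) in Section 8.2 refers back to week 0.
- **Instructions in force.** Section 6 says "Subjects will be asked to avoid extended periods of sun exposure and all use of tanning beds for the duration of the study". Section 5.4 requires "Individuals willing to withhold aesthetic therapies, or other therapies judged to potentially impact results to the treatment areas for the duration of the study".

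**The concern.** Section 3.1 describes a non-randomized, non-controlled study, so the pre-treatment image is the only comparator. If that image is taken on an earlier day than Treatment #1, the measured change covers an untreated period as well as the treated one. Change in the untreated period that persists to follow-up is credited to, or held against, the laser.

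The documents themselves give a route for such a change. Section 1 lists sun exposure among the causes of melasma, and subjects are told to avoid sun and withhold other therapies throughout the study. The start of those instructions is not stated. If they start at Screening, they act before any laser treatment and continue through follow-up.

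Two further points follow. Because combining visits is optional, the gap can differ between subjects within one paired analysis. And an image from two to four weeks before Day 0 is not obviously the week 0 condition to which the PGA refers.

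**Working it through.** **Inputs.** Earliest screening day: -30 (Section 7.1) or -14 (Section 7.3). Visit 2: Day 0 ±3 (Sections 7.1 and 7.4). Visit 3: Day 30 ±3. Visits 4 and 5: 1 and 3 months after treatment, each ±3 days (Section 7.5).

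**Assumptions.** A month is 30 days; follow-up is counted from Treatment #2; the screening image is taken on the earliest day allowed. Nominal Visit 4 is then Day 30 + 30 = 60, and nominal Visit 5 is Day 30 + 90 = 120.

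**Step 1: gap from image to Treatment #1** = Visit 2 day − image day.

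- Visit 2 on Day 0: 0 − (−30) = 30 days, or 0 − (−14) = 14 days.
- Visit 2 on Day +3: 3 − (−30) = 33 days, or 3 − (−14) = 17 days.
- Combined visits: 0 days.

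**Step 2: share of the comparison interval that precedes treatment** = (Visit 2 day − image day) / (follow-up day − image day).

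| Scenario | Window | 1 month | 3 months |
|---|---|---|---|
| Combined visits | either | 0% | 0% |
| All visits nominal (Days 0, 30, 60, 120) | 14 days | 14/74 = 18.9% | 14/134 = 10.4% |
| | 30 days | 30/90 = 33.3% | 30/150 = 20.0% |
| Visit 2 at Day +3, later visits shifted equally (Days 63, 123) | 14 days | 17/77 = 22.1% | 17/137 = 12.4% |
| | 30 days | 33/93 = 35.5% | 33/153 = 21.6% |
| Maximum over all ±3-day windows (Visit 2 Day 3, Visit 3 Day 27, Visit 4 Day 54, Visit 5 Day 114) | 14 days | 17/68 = 25.0% | 17/128 = 13.3% |
| | 30 days | 33/84 = 39.3% | 33/144 = 22.9% |

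The maximum occurs where the gap is longest and the time from Treatment #1 to follow-up is shortest: Visit 4 at Day 27 + 27 = 54 and Visit 5 at Day 27 + 87 = 114.

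**Step 3: meaning of Day 0.** The 33- and 17-day gaps need Day 0 to be a nominal date that Visit 2 can miss. If Day 0 is the actual first treatment, the gaps stop at 30 and 14 days, and the 1-month maximum under the 30-day window is 30/(54 + 30) = 30/84 = 35.7%.

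**Step 4: what is left after Treatment #1.** The smallest post-treatment share is 100% − 39.3% = 60.7%.

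**The case against.** A screening image is a coherent baseline. Only one pre-treatment set is scheduled, so there is no rival image, only a label to tidy. Section 7.3 gives Screening a Day 0 label, the same as Visit 2, and combining the visits is allowed in two places, so many subjects may have no gap at all. Sections 7.4, 8.1, 8.2 and 9 contain redactions, and text may have been removed from 7.3; any of these may define the baseline. The bias is also conditional: it needs separate visits, a long gap, a real untreated change within it, and persistence to follow-up. The percentages are shares of calendar time under earliest-day screening, and the largest needs several windows at their extremes. Most of the interval stays uncontrolled whatever is done.

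Much of this stands. The number of subjects with separate visits is unknown, the effect on pigment cannot be sized from the documents, and hidden text may already say which image is the baseline. But none of it puts an imaging mark at Visit 2 in a table that is fully legible, and none of it reconciles 30 days with 14. If hidden text does call for Visit 2 imaging, the table contradicts that text and still needs correcting. Change after Day 0 cannot be separated without a control group; the part before Treatment #1 can be removed within the present design.

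**Conclusion.** The concern holds. Two things are certain from the legible text: no imaging is scheduled at the visit labelled Baseline, and the two screening windows conflict. The consequence for the result is plausible but unquantified, and its direction is open.

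At nominal days with earliest-day screening, the untreated part is 18.9% to 33.3% of the 1-month interval and 10.4% to 20.0% of the 3-month interval. The extreme over all stated windows is 39.3% at 1 month and 22.9% at 3 months. It is zero for subjects whose visits are combined. These figures rest on the assumptions listed with the calculation and describe time, not pigment.

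Only change that lasts to follow-up is at issue. Change that arises in the gap and reverses before follow-up does not bias a comparison from a Screening image. The point is worth correcting because the correction is cheap, but it does not decide the study's validity.

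**What to change.** 1. In Section 7.1, move the pre-treatment Standard, H2 3D and VISIA set to Visit 2, before the anesthetic and Treatment #1. When Visits 1 and 2 are combined, the single set taken before treatment serves.
2. State that this set is the baseline for every analysis and the week 0 reference for the PGA, unless redacted text already does so.
3. Reconcile the screening windows in Sections 7.1 and 7.3.
4. State as a limitation that change after Day 0 (sun avoidance, season, regression to the mean) remains confounded with treatment. It covers at least 60.7% of the interval in every scenario above.

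**Cost.** No new procedure and no extra imaging for combined visits. For subjects screened on a separate day, Visit 2 (about 1 hour) becomes longer and Visit 1 (30 to 45 minutes) shorter. If the follow-up imaging conditions are applied, the added time includes 15 minutes of acclimation. A short-lived pigment change present on Day 0 would enter the new baseline, so the move protects against lasting change, not against every pattern.

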7.2. Pre-Study Procedures

Prior to the start of the study, potential subjects will be screened for eligibility requirements via chart review on EPIC.

7.3. Screening: Visit 1 (Day 0; -14 to 0 days)

The purpose of the study, eligibility criteria and potential risks will be discussed with the potential subject.

This visit will take 30-45 minutes. Screening (Visit 1) may be combined with Visit 2.

7.4. Treatment Visits: Visit 2 (Day 0; +/-3 days) and Visit 3 (Day 30; +/-3 days)

A member of the study team will record concomitant medications and will ask subjects if they have experienced any changes in their health since the previous visit. If an adverse event (AE) is reported than the Investigator will be informed, and an AE log will be completed/updated for PI review.

The procedure will then be performed in our Plastic Surgery clinic following standard of care procedures. A trained staff member will apply a topical triple anesthetic (benzocaine, lidocaine, tetracaine) to anesthetize the areas being treated. [REDACTED]

Appropriate post-treatment care instructions will be provided as deemed appropriate by the Investigator or study staff. [REDACTED]

These visits will take approximately 1 hour.

7.5. Follow-Up Visits: Visit 4 (1-Month Post Treatment) and Visit 5 (3-Months Post Treatment)

At a minimum, all subjects will return for follow-up visits at 1 month (+/- 3 days) and 3 months (+/-3 days) after treatment.

The following activities will be performed on all study subjects during the follow-up visits:

1. The physician or study staff will ask subjects if they have experienced any changes in their health since the previous visit. Changes will be recorded accordingly. If an adverse event (AE) is reported than the Investigator will be informed, and an AE form will be completed.
 2. Subjects will acclimate to ambient temperature and humidity conditions for 15 minutes prior to any procedures being done.
 3. The physician or study staff will perform an examination of the skin in the treatment area
 4. Obtain post-treatment close up and standard photography as described in section 8.1.
 5. Obtain post-treatment photographs and measurements using the Vectra H2 3D Imaging System and VISIA Imaging System as described in section 8.1.

These visits will take about 30 minutes.

8. Assessments

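### Minor: sections 7.1 and 7.3 give different screening windows, so the only visibly scheduled pregnancy test can be 30 or 14 days old at an on-time Treatment #1 when Visits 1 and 2 are separate

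*Combined protocol and SAP*

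**What the plan says.** The outer limit for Visit 1 appears twice with different values. The column heading in the 7.1 schedule is "Screening (-30 to 0 days". The heading of 7.3, for the same visit, is "Screening: Visit 1 (Day 0; -14 to 0 days".

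The 7.1 table has one mark in the pregnancy test row, at Visit 1, and marks the laser at Visits 2 (Day 0) and 3 (Day 30), each with a 3-day tolerance either way. Inclusion 5 in section 5.4 agrees with that row: "Women of childbearing potential must have a negative urine pregnancy test and must not be lactating at Screening". It asks women to "take a urine pregnancy test at the Screening visit or when deemed by Investigator", so further tests are possible but discretionary. It also requires contraception: "Women must be willing and able to use an acceptable method of birth control (see below) during the study".

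Visits 1 and 2 may be merged. Section 7.3 says "Screening (Visit 1) may be combined with Visit 2", and the footnote to 7.1 says "Treatment #1 (Visit 2) activities may be conducted at the Screening visit (Visit 1".

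The row "H2 3D and VISIA Photography" in 7.1 is marked at Visit 1 and at both follow-up visits. It is not marked at Visit 2, although that column is the one labelled as baseline.

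**The concern.** A screening window is an operative rule: staff book visits by it and a monitor checks against it. With two values, nobody can say whether a subject screened 20 days before the first laser session is compliant or a deviation.

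Two procedures take their timing from that limit. The first is the pregnancy test. By requiring a negative result at entry and birth control throughout, Inclusion 5 shows that the protocol means not to treat pregnant women. A result obtained on the day of treatment serves that aim better than one obtained weeks before, and no visible text says how old the result may be. The second is the set of baseline images. Section 9 bases the primary comparison on Vectra H2 data, and the baseline images are scheduled at Visit 1, so the same limit decides how long before treatment they may be taken.

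At stake are a small gain in participant safety and a consistent visit rule.

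**Working it through.** The plan states no test age, so there is no figure to reproduce. The check is a day count.

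**Inputs**

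- Earliest screening day: Day -30 (7.1) or Day -14 (7.3).
- Treatment #1: Day 0. Treatment #2: Day 30 (7.1 and 7.4).
- Scheduled pregnancy test: Visit 1 only (7.1).

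**Formula**

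Maximum age of the test at a treatment = treatment day minus earliest test day.

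| Situation, visits on schedule | Treatment #1 | Treatment #2 |
|---|---|---|
| Separate visits, 7.1 window | 0 - (-30) = 30 days | 30 - (-30) = 60 days |
| Separate visits, 7.3 window | 0 - (-14) = 14 days | 30 - (-14) = 44 days |
| Visits 1 and 2 combined | 0 - 0 = 0 days | 30 - 0 = 30 days |
| Test moved to Visit 2, before the laser | 0 - 0 = 0 days | 30 - 0 = 30 days |

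**Reading the table**

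- The two windows differ by 30 - 14 = 16 days. The disputed days are -30 to -15.
- Every day from -14 to 0 lies inside both windows, so the shorter window contradicts neither statement.
- Using -14 to 0 in both places, with the test left at Visit 1, gives 14 and 44 days, which is 16 days less than 7.1 allows at each treatment.
- If the test is also moved to Visit 2, its age falls to 0 days at Treatment #1 and to 30 days at an on-time Treatment #2.
- The 3-day tolerance shifts these figures slightly. For example, a Treatment #2 on Day 33 is 33 + 30 = 63 or 33 + 14 = 47 days after the earliest permitted test. The documents give no threshold against which those extra days would matter.
- The Visit 1 images have the same maximum age as the test at an on-time Treatment #1: 30 days under 7.1 and 14 under 7.3. Moving the test does not change this, so the window needs a single value in any case.

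**The case against.** The strongest reply is that the only demonstrable error is a mismatch between two headings, and that the pregnancy test half is a preference. The table schedules what Inclusion 5 asks for, a negative test at screening. No visible text sets a maximum age or asks for a test on the day of treatment, and the visible risk list in section 10 names no fetal hazard. Contraception, health questions at both laser visits and discretionary tests already reduce the risk. The 7.3 heading even labels Visit 1 as Day 0, which suggests that combined visits may be common. Much of this stands, and it is why the point is minor. It does not remove the point: combining is optional, the same heading allows 14 days, and none of the safeguards is a scheduled test.

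A second reply is that the remedy leaves a result about 30 days old at Treatment #2, the same age as the longest on-time interval at Treatment #1 now. That is correct. The change closes the first interval and shortens the second without closing it.

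Third, parts of 5.4 and 7.4 are not visible, including the birth control text that Inclusion 5 points to. Further checks before the laser could be there. The claim therefore covers the visible schedule only. The conflict between the two windows does not depend on hidden text.

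A reader might infer more: that the plan breaches its own pregnancy rule, that it exposes participants to a stated fetal risk, or that ageing baseline images undermine the efficacy result. The documents support none of these. The schedule and Inclusion 5 agree, no fetal risk is stated in the visible text, and nothing in the documents shows that a 14- or 30-day gap alters the image measurements.

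**Conclusion.** The concern holds as a low-severity point. The contradiction is certain: one visit has two outer limits, 16 days apart. As a consequence, with separate visits the only visibly scheduled pregnancy test can be 30 days old (7.1) or 14 days old (7.3) at an on-time Treatment #1.

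These are maxima, not expected values. The documents do not show how often the visits would be separate. With at most 30 subjects and contraception required of women of childbearing potential, few or no pregnancies would be expected in the gap. The conclusion assumes that the visible 7.1 row shows every scheduled pregnancy test. No effect on the efficacy conclusion is claimed.

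**What to change.** 1. Change the Visit 1 column heading in 7.1 to -14 to 0 days. Section 7.3 then needs no edit, and the baseline H2 3D and VISIA images are limited to 14 days before Day 0. Cost: a subject screened 15 to 30 days ahead must be rescreened or scheduled closer to treatment.
2. For women of childbearing potential not yet screened, move the single urine test from Visit 1 to Visit 2, before the laser. Align Inclusion 5 so that the negative result is required on the day of Treatment #1; the lactation check stays at screening. For these women it is the same one test at a different visit, and nothing changes where the visits are combined. Cost: a few women may complete Visit 1 and its photography before being found ineligible. Any woman already tested at Visit 1 but not yet treated would need a second urine test if the change were applied to her.

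A further test at Visit 3 would shorten the remaining interval of about 30 days before Treatment #2. It would be an added procedure, so it is a matter for the investigators and the IRB and is not part of this point.
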